COVER PAGE

Official Title of the Study : Maternal Cognitive Function and Neurobehavioral Development of Underprivileged Children

NCT Number : **NCT03321591**

Date of the Document : **19/09/2016**

Maternal Cognitive Function and Neurobehavioral Development of Underprivileged Children

Introduction

Child development consists of several interdependent domains of sensory-motor, cognitive-language, and social-emotional function (Grantham-McGregor et al., 2007; Walker et al., 2007). Children's development is affected by psychosocial and biological factors through changes in brain structure and function, and behavioral changes (Wachs, 2000). Experiences in the first few years of life are of particular importance because vital development occurs in all the domains during this period, and the interaction between early environments and genetics influences this development and human behavior (Committee on Integrating the Science of Early Childhood Development, 2000). The brain growth occurs rapidly through neurogenesis, axonal and dendritic proliferation, synaptogenesis, cell death, synaptic pruning, myelination, and gliogenesis (Grantham-McGregor et al., 2007). Brain development can be modified by the quality of the environment (Grantham-McGregor et al., 2007). Independent animal research suggests that early under nutrition, iron-deficiency, environmental toxins, stress, and poor stimulation and social interaction can affect brain structure and function (Black et al., 1998; Liu et al., 2000; Meaney, 2001; Morgan et al., 2001; Rodier, 2004; Webb et al., 2001; Wilson et al., 2000). In both humans and animals, variations in the quality of maternal care, a part of home environment, can yield changes in stress reactivity, anxiety (Gunnar, in press), and memory function in the offspring (Grantham-McGregor et al., 2007). In later childhood the affected children will subsequently have lower levels of cognition and education. It is mentionable that remarkable recovery is often possible with early intervention through more nurturing environment with adequate stimulation, despite the vulnerability of the brain to early insults (Black et al., 1998; Bredy, 2003).

It is estimated that over 200 million children under 5 years of age in developing countries (low-income and middle-income countries) are not attaining their developmental potential, primarily because of poverty and associated health, nutritional deficiencies, and unstimulating home environment, and most of them live in south Asia and sub-Saharan Africa (Grantham-McGregor et al., 2007; Walker et al., 2007). Stunting, inadequate cognitive stimulation, iodine deficiency, and iron deficiency anemia are identified as key risk factors, where the need for intervention is urgent, that prevent millions of young children from fulfilling their developmental potential (Walker et al., 2007; Walker et al., 2011). In low-income and middle-income countries, 34% of children younger than 5 years have linear growth retardation or stunting (Walker et al., 2011) resulted from poor nutrition often accelerated by infectious diseases (Walker et al., 2007). It is reported that patterns of growth retardation are identical across countries (Shrimpton et al., 2001). Although the vacillation in growth starts in utero or in the first 12-18 months, continue to around 40 months (Martorell et al., 1995), but most children having stunting remain stunted through to adulthood (Grantham-McGregor et al., 2007). On the other hand, poverty and stunting are identified for indicators

of poor development because they represent different types of biological and psychosocial risks. Poverty is related to inadequate food, and poor sanitation and hygiene that increase infections and stunting in children. Poverty is also connected to poor maternal education, increased maternal stress and depression (Bradley & Corwyn, 2002; Hamadini & Grantham-McGregor, 2004; Baker-Henningham et al., 2003), and deficient stimulation in the home (Schady & Paxson, 2005). All these factors deleteriously affect child development which, in turn, produces poor school achievement, which is further worsened by poor family support (Grantham-McGregor et al., 2007). Risk factors associated with poverty frequently happen together, and degree of development becomes lower with the number of risks factors (Rutter, 1989). Deficits in child development are often occurred in infancy (Feinstein, 2003; Espy et al., 2001) and increase further with age (Richter et al., 1998; Walker & Grantham-McGregor, 1990; Lozoff & Teal, 2004). Several longitudinal studies have found substantial association between socioeconomic status and parental wealth at birth, and cognitive attainment (Sigman et al., 1991; Stein et al., 2005). Poverty and sociocultural background increase children's exposure to psychosocial risks that influence development through behavioral changes (Walker et al., 2007).

Parenting factors like cognitive stimulation or learning opportunities facilitates early cognitive development. Several studies examined the effect of stimulation or intervention on children from developing countries, including children living in poverty, which strongly supports the importance of early cognitive intervention for facilitating better cognitive and non-cognitive outcomes (Grantham-McGregor et al., 1991; Gardner et al., 2003; Eickmann et al., 2003; Kagitcibasi et al., 2001; Magwaza, 1991). Research revealed three aspects of parenting associated to young children's cognitive and social-emotional competence: cognitive stimulation, caregiver sensitivity and responsiveness to the child, and caregiver affect (National Research Council and Institute of Medicine, 2000). Regarding maternal sensitivity and responsivity several researches reported that these factors are associated with more secure infant attachment (Posada et al., 1999; Eomlinson et al., 2005) and higher cognitive ability (Agarwal et al., 1992) respectively. Appropriate caregiver-child interactions facilitate early social-emotional development and learning materials promote age-appropriate language and problem-solving skills (Walker et al., 2007). Furthermore, maternal depression is another risk factor that causes reduced levels of cognitive function and higher levels of behavior problems (Patel et al., 2003). These factors discussed above are the part of maternal cognitive function which implies that there might be a link between factors evolved from maternal cognitive state and child development. Rubalcava and Teruel (2004) showed that maternal cognitive ability works as an important factor in progressing her children's height, even after controlling for child's age and gender, parental age, mother's and father's years of schooling and mother's height.

Iodine deficiency and iron deficiency anemia threatens the development of many children. Recent research highlights the evidence for other risk factors encompassing intrauterine growth restriction, malaria, lead exposure, HIV infection, institutionalization, and exposure to societal violence (Walker et al., 2011). Notably, breastfeeding and higher

maternal education are emerged as protective factors in new research, which attenuate adverse consequences of risk factors that compromise children's development. It is worth mentioning that substantial improvement in development is unlikely to be made without also increasing early learning opportunities (Black et al., 2005), though there has been recent attention to the effect of nutrition on development (Victora et al., 2008). Non-US intervention studies showed that cognitive benefits were better in case of interventions having stimulation and education components compared with those involving nutrition or economic assistance only (Nores & Barnett, 2009). In Bangladesh, research revealed that almost 60% children are exposed to risk of insufficient development caused by high prevalence of LBW (22%), stunting (41%), and poverty (43%), and lack of early stimulation due to low parental knowledge (UNICEF, 2005; Hamadini et al., 2010). Most of the data from developing countries including Bangladesh mainly focused on cognitive and motor outcome with less emphasis on maternal cognitive ability. This is why, in addition to the existing information, we need to assess maternal cognitive ability and neurobehavioral development in order to prepare appropriate intervention particularly for disadvantaged children living in poverty in Bangladesh.

It is clear from the previous studies on poor populations that disadvantaged children require not only good health, nutrition, and wealth but also supportive and caring environments at home and cognitive stimulation in order to achieve their developmental potential as in the case of Bangladesh. According to Lancet review, most disadvantaged children get the maximum benefit of intervention (Engle, 2011). Cognitive function of parents, especially mothers, is crucial for having the optimum outcome from intervention. However, little is known regarding the importance of mother's cognitive functioning influencing different domains of her young children's neurobehavioral developmental outcome mediated by parenting, particularly who are from disadvantaged community in Bangladesh, residing in poverty. We know of no other study, however, that directly emphasizes maternal cognitive function on different domains of development of disadvantaged children in Bangladesh.

We, therefore, plan to examine the association of disadvantaged children's neurobehavioral development i.e., communication, motor skills, problem-solving, and personal-social skills and mother's cognitive function.

Hypothesis: Mothers with better cognitive function will have children with better neurobehavioral development.

Objectives: The specific objectives of the study are (a) to measure the maternal cognitive function, (b) to assess the neurobehavioral development of children.

Methods

Participants

A total of 200 mother-child dyads will participate in the study. Data will be collected by the researcher. Age range of children will range from 12-42 months residing in the slum area located in the city of Dhaka.

Inclusion criteria

Age: 12-42 months on enrolment

Sex: both male and female

Nutritional status: weight-for-age z score (WAZ)>-3SD

Consent: written consent provided by parents

Exclusion criteria

Any child with –

Developmental anomalies,

Known chronic illnesses like epilepsy, tuberculosis,

Twins and multiple births,

Parents not consenting

Sample Size Calculation

Sample size is calculated assuming 5% level of significance, 80% power, an improvement of 0.30 SD neurocognitive developmental scores of children between high and low scorer mother's group, and 15% drop outs, based on the formula below:

$$n = \frac{2(sd)^2}{(M_1 - M_2)^2} \times f(\alpha\beta)$$

Where,

n = sample size per group,

sd=Standard deviation of population=1,

M₁-M₂=Difference between the groups assumed=0.30 SD,

αβ=80% power and 5% significance=8

We need to enroll 150 mother-child dyad.

Measurements

The following measurements will be applied upon all enrolled children's mother:

Bayley Scales of Infant and Toddler Development (BSID-III): Neurobehavioral development of children will be assessed on the revised version of questionnaires of BSID-III. It will be used to assess cognitive, language and motor development of the children. The test has been used in many developing countries, and has been the instrument of choice for child development and nutrition research at this age in other countries like Indonesia and Brazil. It usually takes about an hour to test the children.

The Bangla Adaptation of Mini-Mental State Examination (BAMSE): The Bangla adaptation of Mini-Mental State Examination (BAMSE) will be used to assess the cognitive function of mothers. BAMSE is the Bangla adaptation of Mini-Mental State Examination (MMSE). MMSE (Folstein et al., 1975) is a commonly used brief global instrument that measures cognitive abilities having orientation to time and place, memory and attention, language

skills, and visuo-spatial abilities. A good association ($r=0.57$) was found between the MMSE and BAMSE instruments (Kabir & Herlitz, 2000). Test-retest reliability of BAMSE was satisfactory ($r=0.70$) and BAMSE was found to be less sensitive to age and education than the MMSE (Kabir & Herlitz, 2000).

Anthropometry: Weights, heights, Mid-upper arm circumference (MUAC), and head circumference of all the study children and their mothers will be measured according to standard techniques (Lohman et al., 1989; WHO, 1983). Afterwards these anthropometric measures will be converted into height-for-age (HAZ), weight-for-height (WHZ), and weight-for-age (WAZ).

Socioeconomic status (SES): Information will be obtained on the families' house-hold possessions, standard of housing, family structure, and parental education and occupation. The indices described will be calculated to measure the socioeconomic status of the family: 1) housing, on the basis of the condition of the roof and walls of the house and presence or absence of electricity in the house; 2) sanitation, according to ratings of type of latrine and availability of water inside or outside the house; 3) assets, based on the possession of certain household items; and 4) crowding, composed of the number of people per room.

Procedures

Data Acquisition

Standard data collection procedures will be followed in the study. The author of this research proposal will conduct a house-to-house survey in the study area. At first, the general purpose of the study will be briefed to the parents. After having written consent from the parents, they will be asked for information about their children's development (extended ASQ), and their cognitive function (BAMSI). Anthropometric measures will be taken both for mothers and their children in order to have Body Matched Index (BMI). After administration of the all questionnaires, mothers will be interviewed to obtain information on socio-demographic characteristics. Thus data collection will be completed approximately in three months.

Data Analysis

Participants' responses will be scored according to the scoring systems of the ASQ, BAMSE, and other measures. Data will then be fed to a personal computer and analyzed using the SPSS, version 20. Transformations will be used to normalize the variables when necessary. Data will be analyzed in multiple regression analysis in order to see the relationship between maternal cognitive ability and different domain of child development.

Expected Result and Impact

It is expected that the impact of maternal cognitive function on neurobehavioral development will be considerable.

Although there are few national data for mother's cognitive ability and child's development in Bangladesh, but it can be said that many disadvantaged children are exposed to various

risks for poor development including poverty, malnutrition, poor health and un-stimulating home environment or lack of learning opportunities. Due to poor development, children do poorly in school and subsequently transfer poverty to the next generation. The second UN Millennium goal is to ensure that all children complete primary schooling. The result will help policymakers to take appropriate intervention programs to improve early child development, which, in turn, will achieve satisfactory educational performance. To reach the MDG and to stop the intergenerational transmission of poverty the findings of proposed study will play an important role.

Currently, there are no accepted indicators for child development in Bangladesh. The expected result will help develop country's indicators for child development. Furthermore, the result will provide information to help the setting programs and policies for early childhood development to benefit the disadvantaged children and reduce the persistent inequalities in child development. The proper child development will help make economical and social development of the country.

Time Line

The time plan of the study is described as under

Works	Year								
	1			2			3		
	Quarters			Quarters			Quarters		
	1	2	3	1	2	3	1	2	3
Preparatory works (Manual, SOP, questionnaire preparation)	x								
Site selection	x								
Training		x							
Screening of 1-3.5yr old children & enrolment		x							
Assessment	x	x							
Data entry, cleaning & preliminary analysis			x						
Start writing introduction & method section				x					
Synthesize results & thesis writing					x				
First draft of the PhD thesis						x			
First Seminar							x		

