COVER PAGE

Official Title of the Study : Maternal Cognitive Function and Neurobehavioral Development of Underprivileged Children

NCT Number : NCT03321591

Date of the Document : 19/09/2016

Statistical Analysis Plan: Data will be analyzed by using correlation and multiple regression analysis in order to see the relationship between maternal cognitive function and neurobehavioral development of children. Furthermore, I have a plan to use path analysis (structural equation modeling). In this regard, I have prepared a model to test as under. It is very tough and time consuming to test model fit equation. I have to study more and more on the books of statistics and experts to handle LISREL or SPSS AMOS software.

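### The 80% power claim belongs to a high- versus low-scoring mothers contrast that is neither defined nor listed as an analysis, and for the assumed 0.30 SD neither 150 nor 200 dyads delivers it at any cut-point

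*Protocol*

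**What the plan says.** Under Sample Size Calculation, the protocol assumes 5% significance, 80% power, 15% drop-out and a 0.30 SD difference in "neurocognitive developmental scores of children between high and low scorer mother's group". It uses the usual formula for comparing two means, with n defined per group, "sd=Standard deviation of population=1", and a multiplier given as "80% power and 5% significance=8". It concludes: "We need to enroll 150 mother-child dyad". The Participants section gives a different figure: "A total of 200 mother-child dyads will participate in the study".

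BAMSE is the maternal measure (Measurements section). No median, tertile or score threshold divides mothers into high and low scorers.

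The planned analyses are described differently. The protocol's Data Analysis section says: "Data will be analyzed in multiple regression analysis in order to see the relationship between maternal cognitive ability and different domain of child development". The SAP says: "Data will be analyzed by using correlation and multiple regression analysis", and adds path analysis. Neither lists a comparison of high and low scorers, says whether BAMSE enters as a continuous score or a two-level indicator, or states power for the named analyses.

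**The concern.** There are two linked problems. First, the power statement is attached to a contrast that the plan neither defines nor says it will test. Correcting the arithmetic alone would leave the study powered for a comparison with no groups. Leaving the cut-point open would also allow it to be chosen after the data are seen.

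Second, the claimed 80% does not follow from the protocol's own inputs at either stated sample size.

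The hypothesis is about an association, and the protocol expects the results to inform policy and intervention programmes. A null result credited with 80% power could be read as evidence against an association of the assumed size. The contrast described would miss a true 0.30 SD difference at least 44% of the time, even with 200 evaluable dyads.

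**Working it through.** **Inputs (Protocol, Sample Size Calculation and Participants).** Difference 0.30, SD 1, multiplier 8, 15% drop-out, 150 or 200 dyads. After 15% loss these become 150 × 0.85 = 127.5 (127 used) and 200 × 0.85 = 170.

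**Sidedness.** It is not stated. Two-sided 5% with 80% power gives (1.960 + 0.842)² = 7.85; one-sided gives (1.645 + 0.842)² = 6.18. A multiplier of 8 therefore implies a two-sided test.

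**Step 1: the protocol's formula.**
- n per group = 2 × 1² × 8 / 0.30² = 177.8, rounded up to 178.
- Two groups: 2 × 178 = 356 evaluable.
- With 15% loss: 356 / 0.85 = 418.8, so 419 enrolled.

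The stated 150 is not reproduced. Both stated totals lie near the per-group figure after a drop-out adjustment (178 × 0.85 = 151; 178 × 1.15 = 205). This suggests, as inference only, that a per-group number was used as a total.

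**Step 2: power for 0.30 SD at the stated sizes** (two-sample t-test, two-sided 5%).

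| Split of mothers | 127 | 150 | 170 | 200 evaluable |
|---|---|---|---|---|
| Equal halves | 39% | 45% | 49% | 56% |
| Lowest third versus the rest | 35% | 41% | 45% | 51% |
| Outer thirds only | 28% | 32% | 35% | 41% |

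With the difference held at 0.30 SD, power depends on the split only through n₁n₂/(n₁ + n₂) and the degrees of freedom. With n₁ + n₂ no greater than N, both are largest at n₁ = n₂ = N/2. The first row is therefore a ceiling, and no cut-point restores 80%.

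The smallest difference detectable with 80% power in equal halves is 0.50, 0.46, 0.43 and 0.40 SD respectively.

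**Step 3: the named correlation analysis.** Assume bivariate normality and convert the 0.30 SD.
- Median split: r = 0.30 / (2 × √(2/π)) = 0.188. Two-sided Fisher-z power is 56%, 64%, 69% and 76% at 127, 150, 170 and 200.
- Outer thirds: r = 0.30 / (2 × 1.091) = 0.1375. Power is 34%, 39%, 43% and 49%.

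The unadjusted correlation detectable with 80% power is tanh[(1.960 + 0.842)/√(N − 3)], which gives 0.25, 0.23, 0.21 and 0.20 for one development score.

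**The case against.** **Sidedness.** The hypothesis is directional and no test direction is stated. One-sided, the two-group contrast reaches only 57% at 150 and 68% at 200 before losses. The correlation of 0.188 reaches 79% at 170 and 85% at 200. So a one-sided correlation test with 200 complete dyads would exceed 80%. That reading contradicts the multiplier of 8 and ignores the 15% loss the protocol assumes.

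**Covariate adjustment.** The planned regression may gain precision. For r = 0.188 to reach 80%, covariates unrelated to BAMSE would have to explain 1 − (0.188/0.197)² = 9% of outcome variance with 200 evaluable, 1 − (0.188/0.213)² = 22% with 170, or 1 − (0.188/0.227)² = 31% with 150. With 200 that is plausible. However, covariates that overlap with BAMSE, as socioeconomic measures may, pull the other way, and the protocol makes no such assumption. This stands as a limit on the correlation figures, not on the two-group result.

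**150 as a per-group figure.** The formula defines n per group just before the 150 is stated. A total of 300 would give 74% power, or 67% after 15% loss (255). That is a smaller shortfall, but still below 80%, and it conflicts with the stated total of 200.

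**A fixed 0.30 SD.** A more extreme split would produce a larger true difference if the underlying correlation is fixed. With r = 0.188 the outer thirds differ by 0.188 × 2 × 1.091 = 0.41 SD, and power with 200 is about 65%, not 41%. The split-by-split figures therefore depend on holding 0.30 SD constant, as the protocol does. The conclusion is unchanged.

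**Is the contrast really absent?** A regression with a high/low BAMSE indicator would be that contrast, adjusted. The SAP also refers to a model that does not appear in the text available. The fair statement is that no listed analysis identifies the contrast, and this is the point made here.

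**Conclusion.** The concern holds. The claim of 80% power for 0.30 SD is wrong as written: the protocol's own formula calls for 356 evaluable dyads, against stated totals of 150 and 200. At best, two-sided power is 45% or 56% without losses and 39% or 49% after 15% loss. The contrast it describes has no cut-point and is not identified in either analysis section.

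This rests on the protocol's own difference and SD, on a two-sided test as its multiplier implies, and on 150 and 200 being totals. For the correlation analysis the shortfall is smaller (64% to 76% with 150 to 200 evaluable, for the median-split equivalent). Those figures also need bivariate normality and no covariate adjustment.

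**What to change.** 1. Reconcile 150 with 200, and say whether the figure is enrolled or evaluable.

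2. Replace the two-group power statement with the effect detectable in the planned analysis, with BAMSE as a continuous score. For example: *With 200 enrolled and 15% loss (170 evaluable), the study has 80% power at two-sided 5% to detect an unadjusted correlation of 0.21 between BAMSE and one development score; power for the adjusted regression coefficient depends on how far the covariates overlap with BAMSE and the outcome.* If 150 are enrolled (127 evaluable), the figure is 0.25.

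3. If a high/low comparison is really intended, define the BAMSE cut-point in advance, list the comparison as an analysis in both documents, and restate its power at the chosen sample size.

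The cost is one protocol paragraph and one SAP sentence, with no change to data collection. The downside is a less favourable stated power.

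### The protocol's sample size formula gives 178 dyads per group (356 evaluable, about 419 enrolled), not 150 or 200; the two-group comparison it sizes has about 39–56% power at 0.30 SD, not 80%

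*Protocol*

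**What the plan says.** The Sample Size Calculation section of the protocol sets the error rates first: "Sample size is calculated assuming 5% level of significance, 80% power". It then gives the effect and the attrition: "an improvement of 0.30 SD neurocognitive developmental scores of children between high and low scorer mother's group, and 15% drop outs". The formula is the usual one for comparing two means, n = 2·sd² / (M₁ − M₂)² × f(α,β), with these definitions:

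- "n = sample size per group"
- "sd=Standard deviation of population=1"
- "M₁-M₂=Difference between the groups assumed=0.30 SD"
- "αβ=80% power and 5% significance=8"

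No substitution is shown. The section ends with "We need to enroll 150 mother-child dyad". Shortly before, the Participants section says "A total of 200 mother-child dyads will participate in the study". Neither total is explained by reference to the other, and the SAP gives no sample size.

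**The concern.** Every input is printed, so the answer can be checked directly. The stated 150 is smaller than the 178 the formula requires for one group, before any allowance for drop-out. Two things are at stake.

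The first is how the result will be read. The protocol presents the study as having 80% power for a 0.30 SD difference and expects the findings to inform policy on early child development. If the real power is near one half, a null result says little about a difference of that size, yet readers would take it as evidence against the hypothesis.

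The second is the target itself. With 150 in one section and 200 in another, nobody can say when recruitment is complete or which number the power statement describes.

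**Working it through.** **Inputs, all from the Sample Size Calculation section:** sd = 1; difference = 0.30 SD; f = 8; n is per group, with two groups; drop-out 15%. Sidedness is not stated, but f = 8 is the rounded two-sided value: (1.96 + 0.8416)² = 7.85. The group ratio is not stated; the factor 2 in the formula implies equal groups.

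**Step 1. Attempt to reproduce the stated 150.**

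- n per group = 2 × 1² / 0.30² × 8 = 16 / 0.09 = 177.8, rounded up to 178
- Evaluable total = 2 × 178 = 356
- Enrolled = 356 / 0.85 = 418.8, rounded up to 419 (the shortcut 356 × 1.15 = 409.4 gives 410)

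Neither 150 nor 200 results; 150 is about 36% of 419.

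**Step 2. Alternative readings.**

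| Reading | Per group | Evaluable total | Enrolled |
|---|---|---|---|
| As printed, f = 8 | 178 | 356 | 419 |
| Exact two-sided f = 7.85 | 175 | 350 | 412 |
| One-sided 5% (contradicts f = 8) | 138 | 276 | 325 |

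Reading 150 as a per-group figure also fails: it is below 178, and the power would be 74%, or 67% after 15% loss. Reading n as the total contradicts its printed definition, and 178 evaluable still exceeds 150.

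**Step 3. Where the totals might come from.** Several routes land close by. A difference of 0.50 SD gives 2 × 8 / 0.25 = 64 per group, and 2 × 64 / 0.85 = 150.6. A difference of 0.40 SD with no drop-out gives 2 × 8 / 0.16 = 100 per group, so 200. Treating the per-group 178 as a total gives 178 × 0.85 = 151.3 and 178 × 1.15 = 204.7. The documents do not say which route, if any, was used, and the conclusion does not depend on it.

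**Step 4. Power at 0.30 SD for the two-group comparison** (two-sided 5%, equal groups). The normal approximation is Φ(0.30 × √(n/2) − 1.96), with n per group; the t column uses the noncentral t distribution.

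| Dyads analysed | Normal | t-test |
|---|---|---|
| 127.5 (150 enrolled, 15% lost) | 39.5% | 39.0% |
| 150 | 45.1% | 44.6% |
| 170 (200 enrolled, 15% lost) | 49.8% | 49.4% |
| 200 | 56.4% | 56.0% |
| 356 | 80.8% | 80.6% |

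The last row confirms that the formula delivers 80% power at the size it actually calls for. One-sided testing would give 52% to 68% across the first four rows.

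**Step 5. Difference detectable with 80% power,** √(2 × 8 / n per group):

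- 150 enrolled, 15% lost: √(16 / 63.75) = 0.50 SD
- 150 analysed: √(16 / 75) = 0.46 SD
- 200 enrolled, 15% lost: √(16 / 85) = 0.43 SD
- 200 analysed: √(16 / 100) = 0.40 SD

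**Step 6. Power for a correlation, closer to the planned analysis.** Assume bivariate normality and a median split of the maternal score. A 0.30 SD difference between halves then corresponds to the ρ that solves 2√(2/π)·ρ / √(1 − 2ρ²/π) = 0.30, which is ρ = 0.186. Unadjusted two-sided power is Φ(atanh(ρ)·√(N − 3) − 1.96): 55% at N = 127, 63% at 150, 68% at 170 and 75% at 200. Reaching 80% takes about 225 evaluable dyads.

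**The case against.** The strongest counter-argument is that the 39–56% is not the power of the analysis that will be run. The protocol's Data Analysis section plans multiple regression, and the SAP plans correlation, regression and path analysis. Neither contains a test of high against low scorers. Using the full maternal score wastes less information than splitting it, and under the model in Step 6 power is 55–75%. That point stands, and the lower range must be labelled as belonging to the two-group comparison. It does not rescue the plan: the claimed 80% is itself a claim about that comparison, no other sample size justification is given, and the correlation figures are also below 80%. Covariate adjustment could move them either way.

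Two further points stand in part. The house-to-house survey describes no follow-up visit, so drop-out may be small and the 39% and 49% are the pessimistic end. The protocol nevertheless assumes 15%, and with no loss at all power is still only 45% or 56%. Also, equal groups are an assumption, because no cut-point for high and low scorers is given; unequal groups would lower power further.

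**Conclusion.** The concern holds. The printed inputs require 178 per group, 356 evaluable and about 419 enrolled; the stated 150 and 200 do not follow from them and contradict each other. At those totals a 0.30 SD difference between two equal groups would be missed 44% to 61% of the time at the two-sided 5% level, against the 20% implied by the stated power. The range runs from 200 dyads with no loss to 150 with 15% loss. The sample size error and the conflict between totals rest only on the protocol's own text. The power range also assumes two-sided testing and equal groups, and the correlation figures further assume bivariate normality, a median split and no covariates.

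**What to change.** Choose one enrolment number, use it in both the Participants and Sample Size Calculation sections, and delete the other. Then make the power statement match it:

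- **If 200 is kept:** state that 15% loss leaves 170 evaluable dyads, giving 80% power for 0.43 SD and 49% for 0.30 SD in a comparison of equal halves.
- **If 150 is kept:** state that after 15% loss it can detect 0.50 SD with 80% power and has 39% power for 0.30 SD. Present 0.50 SD as what the number can detect, not as its rationale, because the documents give no basis for that effect size.
- **If 80% power at 0.30 SD must be kept for the two-group comparison:** the protocol's formula calls for about 419 enrolled.

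In each case show the substitution into the formula, state sidedness and the cut-point, and add a sentence on power or precision for the planned regression. With 170 evaluable dyads, for example, an unadjusted correlation of about 0.19 has 68% power under the Step 6 assumptions.

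The first two options change wording in two protocol paragraphs and need no additional dyads beyond the number kept. Their price is a less favourable power statement. Only the third increases enrolment.
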